## 6.4.2 Prohibited Therapies or Procedures

**Table 3** lists prohibited medications that are not to be used from the defined washout periods before the first administration of study products at the Day 1 visit through the last study visit.

The discretionary use of concomitant treatments or therapies for atopic dermatitis is prohibited between Day 1 and Week 16 visit. However, should subjects experience an exacerbation of atopic dermatitis that requires, in the opinion of the investigator, the use of a prohibited therapy, the following approach should be followed:

1. The investigator needs to discuss the case with the medical monitor in order to obtain permission to use a prohibited medication.
2. Subjects who start prohibited medications as a treatment for AD within the first 4 weeks of the study will be discontinued from the study product (ASN002 or placebo) and will perform the ET visit at the time of discontinuation. In addition, the subject will be asked to come back for a follow-up visit 4 weeks after the study product is stopped. Collection of PD samples, PK samples, and skin biopsies will not be performed after the ET visit. These subjects will not be eligible to participate in the OLE study.
3. Subjects who start prohibited topical medications as a treatment for AD after the first 4 weeks of the study may continue all the study assessments up to the last study visit. Treatment with the study product may continue concurrently until the end of the treatment period, and these subjects will be eligible to participate in the OLE study afterwards. Collection of PD samples and skin biopsies will not be performed after the start of a topical medication.
4. Subjects who start prohibited oral corticosteroids as a treatment for AD after the first 4 weeks of the study will be discontinued from the study product (ASN002 or placebo). Use of oral corticosteroids after permanent cessation of ASN002 is permitted only for a short period of time (maximum 3 weeks). Subjects should come to all planned study visits for safety assessments up to the Week 12 visit. Collection of PD samples, PK samples, and skin biopsies will not be performed after study product discontinuation. These subjects will be eligible to participate in the OLE study if they meet the required washout period for prohibited medications as defined in the OLE study.

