6.2 Handling of Dropouts or Missing data

See Appendix 2 for handling of completely or partially missing dates for prior and concomitant medications and adverse events.

For safety analyses, no imputation of the data will be done and analyses will be conducted on the observed cases (OC). All efficacy analyses will be performed using Mixed Model Repeated Measures (MMRM) analyses as primary analyses to take care of missing observations. (See section 12.1).

For subjects starting prohibited medications as listed in section 6.4.2 of the protocol, all efficacy data captured after the start of prohibited medication will be considered missing for the analysis

	STATISTICAL ANALYSIS PLAN, Version Final 2.0
Protocol Number: ASN002AD-201 V3.0	Sponsor: Asana BioSciences, LLC

of those parameters. A sensitivity analysis on the primary endpoint EASI will be done including all efficacy EASI data for these subjects (before and after the prohibited medication).

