Additional exploratory analyses may be performed to further understand the impact, if the results of the sensitivity analyses excluding the subjects for whom the IGA form was initially used to capture the vIGA assessment at baseline reveal inconsistencies with the results including those subjects.

The time to achieve the 50%, 75%, or 90% reduction in EASI relative to baseline and the time to achieve a 4-point reduction from baseline in weekly average of the peak daily pruritus NRS will be compared between treatments using the Kaplan Meier method. A subject will be considered as censored if he has not met the event of interest at the end of the study (Week 12 visit) or if the subject is lost to follow up at last observation. Those subjects will be censored at their last available EASI (or NRS) assessment.

Information for stratification factors will be taken from the EDC database, and not the IWRS for all secondary endpoint analyses.

Descriptive statistics will be presented on all secondary endpoints by visit and treatment group.

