Frequency and percentage of subjects who experience TEAE will be summarized by SOC, PT, and relationship. A treatment-related TEAE is defined as any TEAE that is assessed by the investigator as probably or possibly related to study treatment. TEAE that is assessed as not related

	STATISTICAL ANALYSIS PLAN, Version Final 2.0
Protocol Number: ASN002AD-201 V3.0	Sponsor: Asana BioSciences, LLC

will be defined as not treatment-related. If a subject experience more than one TEAE within different relationship categories within the same SOC/PT, only the worst case (greatest reported relationship) will be reported. A TEAE with an unknown relationship will be considered as treatment-related.

Frequency and percentage of subjects who experience TEAE will be summarized by SOC, PT, and severity (mild/moderate/severe). If a subject experience more than one TEAE within different severity categories within the same SOC/PT, only the worst case (highest reported severity) will be reported. TEAE with an unknown severity will be considered as severe.

Frequency and percentage of subjects will be summarized by SOC, PT, relationship, and severity (mild/moderate/severe). Each subject will be counted only once within a System Organ Class or a Preferred Term by using (1) the greatest reported relationship followed by (2) the highest reported intensity. TEAE with an unknown severity will be considered as severe.

Frequency and percentage of subjects who experience TEAE of clinical relevance and TEAE of clinical interest will be summarized by SOC and PT within SOC.

Frequency and percentage of subjects who experience serious TEAE will be summarized by SOC and PT within SOC.

Frequency and percentage of subjects who experience serious TEAE will be summarized by SOC, PT, and relationship. If a subject experience more than one TEAE within different relationship categories within the same SOC/PT, only the worst case (greatest reported relationship) will be reported.

Proportion of subjects withdrawing from worsening AD will be summarized at Weeks 2, 4, 8, and 12. Furthermore, the time to onset, duration and time to onset greater than or less than 4 weeks of the most frequent TEAEs, defined as the 1% most prevalent TEAEs, will be summarized.

Listings of all AEs, all AEs leading to death, all serious AEs, all TEAEs leading to study drug discontinuation, all TEAEs leading to study discontinuation, and all most frequent TEAEs will be provided.

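### The time-to-response analyses censor subjects rescued for an AD exacerbation, or withdrawn for worsening AD, as if they could still respond, so Kaplan-Meier overstates response without rescue.

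*SAP*

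**What the plan says.** SAP 12.2 (Secondary Endpoint Analyses) compares these times between treatments by the Kaplan-Meier method and names no test. The censoring rule has three parts:

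- No event by Week 12: "A subject will be considered as censored if he has not met the event of interest at the end of the study".
- Loss to follow-up: "or if the subject is lost to follow up at last observation".
- Time of censoring: "Those subjects will be censored at their last available EASI (or NRS) assessment".

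Neither rescue nor withdrawal for worsening AD is mentioned. SAP 6.2 supplies the rest for subjects who start a prohibited medication: "all efficacy data captured after the start of prohibited medication will be considered missing for the analysis".

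Protocol 6.4.2 describes when AD rescue is used: "should subjects experience an exacerbation of atopic dermatitis that requires, in the opinion of the investigator, the use of a prohibited therapy". Follow-up need not stop at rescue, since subjects "who start prohibited topical medications as a treatment for AD after the first 4 weeks of the study may continue all the study assessments". Withdrawal for worsening AD is foreseen, but only as a safety summary (SAP 13.1): "Proportion of subjects withdrawing from worsening AD will be summarized at Weeks 2, 4, 8, and 12".

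Protocol 8.3.1 left the handling of missing values in subjects who start prohibited medications to the SAP. The only sensitivity analysis on this point concerns the primary endpoint (SAP 6.2): "A sensitivity analysis on the primary endpoint EASI will be done including all efficacy EASI data for these subjects". None is planned for the time-to-event endpoints.

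**The concern.** Kaplan-Meier assumes that a subject censored at a given time has the same later chance of the event as those still followed. Here a subject can leave the risk set because the disease flared enough to need other treatment, which marks someone less likely to reach EASI50, EASI75 or EASI90. The estimator then assigns that subject the later response rate of those who remained well enough to stay unrescued.

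At stake is what the curves mean. A reader will take the Week 12 value as the proportion who reached the threshold on assigned treatment. It will be higher than that proportion wherever non-responders were rescued and later responses occurred. The distortion will differ between arms if rescue or later response differs.

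**Working it through.** **The plan's own figures.** The documents state no figure for these endpoints. The sample-size figures in SAP 5.1 reproduce and are untouched:

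- Difference 7, SD 8, two-sided alpha 0.0167, 40 per group: 92.6% power by the noncentral t (stated 92%).
- 37.5% vs 11.1%, 46 per group, alpha 5%: 80.0% by Fisher's exact test (stated 80%).
- 46/0.85 = 54.1, rounded up to 55 per group.

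**How the rules combine.** Take a subject below EASI50 at Week 4 who starts a topical AD medication before Week 8 and attends to Week 12. SAP 6.2 removes the Week 8 and Week 12 values. The last available EASI is Week 4, so SAP 12.2 censors there.

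**Example per 100 subjects per arm (all rates assumed).** Rescue or AD withdrawal falls between Weeks 4 and 8.

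- Placebo: 15 respond by Week 4, 25 are rescued or withdraw, then 10 respond at Week 8 and 10 at Week 12. Kaplan-Meier: 1 − (85/100)(50/60)(40/50) = 43.3%. Response without rescue: 35/100 = 35%.
- Active: 35 respond, 5 are rescued, then 20 and 10 respond. Kaplan-Meier: 1 − (65/100)(40/60)(30/40) = 67.5%. Response without rescue: 65%.
- Difference: 24.2 points by Kaplan-Meier, 30 without rescue.
- With 15 placebo rescues instead of 25: 1 − (85/100)(60/70)(50/60) = 39.3% against 35%, and a difference of 28.2 points.

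**At the planned evaluable size, 46 per arm (rates assumed).**

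- Placebo: 2, 3, 3 and 3 responders at Weeks 2, 4, 8 and 12, with 14 rescued after Week 4. 1 − (41/46)(21/27) = 30.7% against 11/46 = 23.9%.
- Active: 6, 9, 8 and 5 responders, with 4 rescued. 1 − (31/46)(14/27) = 65.1% against 28/46 = 60.9%.
- Difference: 34.4 points by Kaplan-Meier, 37.0 without rescue.

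**Range over assumed rates.** Let F be the Kaplan-Meier response at Week 12 and R the cumulative rescue risk among non-responders. Spread F evenly over the four visits, h = 1 − (1−F)^(1/4), and R over the three intervals between them, r = 1 − (1−R)^(1/3). With q = (1−h)(1−r), response without rescue is h(1 + q + q² + q³). For F = 0.40 and R = 0.30: h = 0.120, r = 0.112, q = 0.78, giving 34.4%.

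| Assumed case (rescue risk placebo / active) | Placebo: KM / without rescue | Active: KM / without rescue | Difference: KM / without rescue |
|---|---|---|---|
| EASI50-like (30% / 10%) | 40.0 / 34.4 | 80.0 / 77.2 | 40.0 / 42.8 |
| EASI75-like (40% / 20%) | 20.0 / 16.0 | 55.0 / 50.3 | 35.0 / 34.3 |
| EASI90-like (30% / 10%) | 8.0 / 6.8 | 35.0 / 33.4 | 27.0 / 26.6 |
| EASI90-like (40% / 20%) | 8.0 / 6.3 | 35.0 / 31.7 | 27.0 / 25.4 |

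With rescue risk of 20–50% on placebo and 10–20% on active, the overstatement in points is:

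- EASI50-like: 3.7–9.7 placebo, 2.8–5.6 active.
- EASI75-like: 2.0–5.1 placebo, 2.3–4.7 active.
- EASI90-like: 0.8–2.1 placebo, 1.6–3.3 active.

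Over 9,702 combinations with higher response on active and more rescue on placebo, the placebo arm had the larger relative overstatement in all of them, but the larger overstatement in percentage points in only 58%. The NRS endpoint was not modelled separately.

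**The case against.** The strongest reply is about the question being asked. SAP 6.2 sets post-rescue data to missing for efficacy analyses generally, and censoring at rescue follows that approach. If the target is response had no rescue been given, 35% is not the truth in the example. The gap to 43.3% then does not measure bias, because Kaplan-Meier is wrong only so far as rescue predicts later non-response. That stands as a limit on the numbers. It does not clear the method, because a trigger based on exacerbation makes such prediction likely, and the SAP does not say that a no-rescue question is intended for these endpoints.

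The reply can add that the rule names neither rescue nor AD withdrawal. This is correct. Rescue follows from reading SAP 12.2 with SAP 6.2. A subject withdrawing for worsening AD is not lost to follow-up as Protocol 5.3.2 defines it (unable to be contacted), but has no event and the SAP offers no other treatment.

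SAP 6.2 also says that MMRM handles missing observations in all efficacy analyses. MMRM does not apply to a Kaplan-Meier endpoint.

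Two stronger readings are tempting and not supported:

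- That the placebo curve is inflated most, so the drug effect is understated. The documents give no rescue rate by arm. Even with more rescue on placebo, the point overstatement can be larger on active, and the difference can grow (25.4 to 27.0 in the table).
- That a mismatch with the by-visit responder proportions would expose the fault. First achievement and response at a visit differ anyway when a subject responds and relapses.

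**Conclusion.** The point holds. Read together, SAP 12.2 and 6.2 censor rescued non-responders at the last pre-rescue assessment, and withdrawals for worsening AD are censored by default. This overstates the share who respond without rescue, and probably also misstates a no-rescue question.

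The size is unknown. The assumed cases give about 1 to 10 points per arm, counting rescue as failure. The relative overstatement tends to be larger in the arm with more rescue, but the direction of the error in the treatment difference cannot be predicted, so the rule cannot be defended as conservative.

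The consequence is limited. These are secondary endpoints with nominal p-values (SAP 6.5). The primary analysis, its rescue sensitivity analysis and the sample size are unaffected. The change is worth making but is not critical.

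**What to change.** In SAP 12.2, treat start of a prohibited AD medication, or withdrawal for worsening AD, before the threshold is reached as a competing event, and report cumulative incidence by arm. Keep ordinary censoring for loss to follow-up and for withdrawals unrelated to AD. Keep the present rule as a sensitivity analysis.

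A simpler alternative is to keep these subjects at risk as non-achievers to the end of the Week 12 analysis window, Day 87 (SAP 5.4), or to use nominal visits with censoring after the Week 12 events. This approximates cumulative incidence and is not exactly equal when other censoring occurs.

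The day matters. Take the 25-rescue placebo example and assume Week 12 visits split evenly between Days 83 and 86, with 5 responses on each:

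- Non-achievers held to Day 84: 1 − 0.75(70/75)(20/25) = 44%.
- Non-achievers held to Day 87: 1 − 0.75(70/75)(45/50) = 37%, because the 20 non-responders seen on Day 83 are still censored that day.
- Nominal visits: 1 − (85/100)(75/85)(65/75) = 35%.

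Nominal visits are therefore the safer time scale, for cumulative incidence as well.

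The cost is SAP wording and minor programming. Medication start dates and indications (Protocol 6.4) and withdrawal reasons (Protocol 5.3) are already collected. The endpoint becomes time to response without rescue, and the curves will be somewhat lower. The rule should be fixed before unblinding, because a choice made after seeing rescue by arm would be open to challenge.

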13 SAFETY ANALYSIS

All safety analyses will be conducted using the safety population.

13.1 Adverse Events

Adverse events (AEs) will be coded according to the Medical Dictionary for Regulatory Activities (MedDRA), Version 21.0.

Treatment emergent adverse event (TEAE) is any condition that was not present prior to treatment with the study product but appeared following treatment, was present at treatment initiation but worsened during treatment, or was present at treatment initiation but resolved and then reappeared while the individual was on treatment (regardless of the intensity of the AE when the treatment was initiated). See Appendix 2 for handling of completely or partially missing dates for AEs. In the case where it is not possible to define an AE as treatment emergent or not, the AE will be classified as treatment emergent.

	STATISTICAL ANALYSIS PLAN, Version Final 2.0
Protocol Number: ASN002AD-201 V3.0	Sponsor: Asana BioSciences, LLC

An overall summary table of adverse events will be provided. The number of events and the number and percentage of subjects who experienced AE, TEAE, TEAE by greatest reported relationship, TEAE by relationship, TEAE by highest reported severity, TEAE by severity, related TEAE by highest reported severity, related TEAE by severity, serious AE, serious TEAE, serious TEAE by greatest relationship, TEAE and related TEAE leading to study drug discontinuation, TEAE and related TEAE leading to study discontinuation, TEAE and related TEAE leading to treatment interruption and AE leading to death will be presented as well as TEAE of clinical relevance and of clinical interest.

TEAE of clinical relevance are:

- Neutropenia
- Lymphopenia
- Eosinopenia
- CPK elevation
- Headache
- Nausea
- Nasopharyngitis
- Diarrhea
- Vomiting

TEAE of clinical interest are:

- Thrombosis (deep venous thrombosis, pulmonary embolism, and arterial thrombosis)
- Anemia
- Arthralgia

Unless otherwise specified, a subject experiencing the same TEAE multiple times will be counted only once for the corresponding PT. Similarly, if a subject experiences multiple TEAEs within the same SOC, the subject will be counted only once for that SOC. TEAEs will be sorted alphabetically by SOC and within each SOC the PT will be presented by decreasing order.

Frequency and percentage of subjects who experience TEAE will be summarized by SOC and PT within SOC.

Frequency and percentage of subjects who experience TEAE will be summarized by SOC, PT, and relationship. A treatment-related TEAE is defined as any TEAE that is assessed by the investigator as probably or possibly related to study treatment. TEAE that is assessed as not related

	STATISTICAL ANALYSIS PLAN, Version Final 2.0
Protocol Number: ASN002AD-201 V3.0	Sponsor: Asana BioSciences, LLC

will be defined as not treatment-related. If a subject experience more than one TEAE within different relationship categories within the same SOC/PT, only the worst case (greatest reported relationship) will be reported. A TEAE with an unknown relationship will be considered as treatment-related.

Frequency and percentage of subjects who experience TEAE will be summarized by SOC, PT, and severity (mild/moderate/severe). If a subject experience more than one TEAE within different severity categories within the same SOC/PT, only the worst case (highest reported severity) will be reported. TEAE with an unknown severity will be considered as severe.

Frequency and percentage of subjects will be summarized by SOC, PT, relationship, and severity (mild/moderate/severe). Each subject will be counted only once within a System Organ Class or a Preferred Term by using (1) the greatest reported relationship followed by (2) the highest reported intensity. TEAE with an unknown severity will be considered as severe.

Frequency and percentage of subjects who experience TEAE of clinical relevance and TEAE of clinical interest will be summarized by SOC and PT within SOC.

Frequency and percentage of subjects who experience serious TEAE will be summarized by SOC and PT within SOC.

Frequency and percentage of subjects who experience serious TEAE will be summarized by SOC, PT, and relationship. If a subject experience more than one TEAE within different relationship categories within the same SOC/PT, only the worst case (greatest reported relationship) will be reported.

Proportion of subjects withdrawing from worsening AD will be summarized at Weeks 2, 4, 8, and 12. Furthermore, the time to onset, duration and time to onset greater than or less than 4 weeks of the most frequent TEAEs, defined as the 1% most prevalent TEAEs, will be summarized.

Listings of all AEs, all AEs leading to death, all serious AEs, all TEAEs leading to study drug discontinuation, all TEAEs leading to study discontinuation, and all most frequent TEAEs will be provided.

13.2 Clinical Laboratory

Descriptive statistics will be presented for data related to chemistry, hematology and quantitative urinalysis. Change from baseline values will be presented for each post-baseline assessment. Frequencies and percentages for each result will be provided for qualitative urinalysis data.

	STATISTICAL ANALYSIS PLAN, Version Final 2.0
Protocol Number: ASN002AD-201 V3.0	Sponsor: Asana BioSciences, LLC

Shift tables from baseline to each post-baseline visits and to each timepoint describing shifts to abnormality will be provided as well. Only subjects with a baseline result and a result at the specified visit for the parameter will be considered.

Separate listings of all data for chemistry, hematology, urinalysis, serology and pregnancy test will be provided.

In addition, separate listings of data for chemistry, hematology, and urinalysis will be provided for each parameter where a subject had at least one abnormal result.

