5.7 Handling of Retests, Unscheduled Visits, and Early Termination Data

When retests measurements are done, the retest measurement will be considered for the summary analysis. All data from retest visits will be listed.

For safety data, unscheduled measurements will not be summarized in by-visit summary tables or figures. However, data from unscheduled visits will be listed. Early Termination (ET) visit assessments will be summarized as a separate visit in by-visit outputs.

For efficacy data, unscheduled measurements and ET visit assessments will be re-mapped according to the windowing conventions in section 5.4.

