7 STUDY SUBJECTS

7.1 Disposition of Subjects

All subjects who provide informed consent will be accounted for in this study. The number of subjects screened and subjects rescreened will be presented. Screen failures will be presented for all screened subjects except for those who were rescreened and did not fail the second screening. Moreover, the number of subjects randomized included in each population will be presented. Study completion status and the reason for study discontinuation will also be presented. Number of subjects using therapy on study up to Week 12 and the number of subjects continuing into the open label extension are also presented. Percentages will be calculated using the number of subjects randomized as denominator. Number of days in the study will be calculated as follows and will be summarized:

$$\text{Number of days in study} = \text{Date of completion/discontinuation} - \text{1}^{\text{st}} \text{ dose date} + 1$$

A listing of subject's disposition will be provided. Information on first screening for subjects who were rescreened, including the rescreened subject identifier, will be presented under the first

	STATISTICAL ANALYSIS PLAN, Version Final 2.0
Protocol Number: ASN002AD-201 V3.0	Sponsor: Asana BioSciences, LLC

screening subject identifier. A listing of subject's randomization information and a listing of subjects included in each of the study populations will also be provided.

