11 STUDY TREATMENT EXPOSURE AND TREATMENT COMPLIANCE

A summary of exposure will be presented using the safety population for each treatment group and will include descriptive statistics of the number of days treated for each treatment group. For each treatment, compliance will be calculated as follow:

$$\frac{\text{Number of dose taken}}{\text{Number of days between the last dose date and the first dose date} + 1} \times 100$$

Descriptive statistics for the compliance will be presented for each treatment group. Frequency distribution will also be presented for the following categories: < 80%, [80% - 120%] and > 120%.

Exposure and compliance will be displayed in a listing of study treatment administration.

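### SAP 13.2 specifies no per-arm count of subjects who reach the protocol's laboratory hold or stop limits, and SAP 5.7 can take a triggering value out of the by-visit summaries

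*SAP*

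**What the plan says.** **Limits.** Protocol 4.4.1 interrupts drug, until laboratory retesting and/or resolution, for neutrophils above 0.5 but below 1, platelets above 50 but below 100, lymphocytes above 0.2 but below 0.5 (all x10^3/µL), CPK above 10 x ULN, or AST/ALT above 5 x ULN. Protocol 4.4.2 ends participation for neutrophils at or below 0.5, lymphocytes at or below 0.2, or platelets at or below 50.

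**Laboratory outputs.** SAP 13.2 plans descriptive statistics and change from baseline by visit, listings, and shifts: "Shift tables from baseline to each post-baseline visits and to each timepoint describing shifts to abnormality will be provided as well". Protocol 8.3.3 asks only for descriptive statistics by treatment and visit.

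**Which values enter the summaries.** SAP 5.7 states: "When retests measurements are done, the retest measurement will be considered for the summary analysis". It adds: "For safety data, unscheduled measurements will not be summarized in by-visit summary tables or figures". For early termination (ET), "visit assessments will be summarized as a separate visit in by-visit outputs".

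**Other outputs.** SAP 13.1 has a list headed "TEAE of clinical relevance are", which includes neutropenia, lymphopenia and CPK elevation, and it says: "Frequency and percentage of subjects who experience TEAE of clinical relevance and TEAE of clinical interest will be summarized". It also tabulates all TEAEs by system organ class and preferred term, and counts TEAEs leading to interruption or discontinuation. In SAP 7.1, "Study completion status and the reason for study discontinuation will also be presented". The exposure summary in SAP 11 "will include descriptive statistics of the number of days treated for each treatment group", together with compliance.

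**The concern.** Changes in safety laboratory tests are a stated secondary safety endpoint, and the protocol has already named the values it regards as serious enough to hold or stop drug. The obvious question about a three-dose trial is how many subjects on 40, 60 or 80 mg, against placebo, reached those values. No output described in the SAP answers it.

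The rule on retests adds a possible distortion. The subjects most likely to be retested are those who crossed a limit, and by then the drug has been withheld. If the drug caused the abnormality and it reverses off drug, the summarized value looks better than the value that led to action.

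**Working it through.** No figure in the plan is in dispute, so the check sets the provisions side by side.

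**1. Limits against planned laboratory tables.** There are 5 hold limits and 3 stop limits, 8 in all. SAP 13.2 refers to none of them. By-visit minimum and maximum (SAP 5.5) can show that some summarized value crossed a limit, but not in how many subjects.

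**2. Shift tables.** The SAP does not define abnormality. If the categories are simply normal and abnormal, which is an assumption because the layouts are elsewhere, entry rules matter. Exclusion criterion 16 removes subjects with AST/ALT above 2 x ULN at screening and sets no CPK limit. A subject who enters with AST/ALT between 1 and 2 x ULN, or with raised CPK, and later passes 5 x or 10 x ULN would be abnormal at both times and show no shift. Shifts are also by visit, with no worst-value category.

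**3. What SAP 5.7 does to a triggering value.**

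| How the value arises | By-visit tables | Listings |
|---|---|---|
| Scheduled visit, repeat treated as that visit's retest | Replaced by the retest | Kept |
| Scheduled visit, repeat booked as unscheduled | Kept | Kept |
| Unscheduled draw | Left out | Kept |
| ET visit | Kept, as its own visit | Kept |

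The SAP does not say whether a repeat drawn on a later date is a retest or an unscheduled value, so the choice between the first two rows rests on coding. The rows are possibilities of unknown frequency; counting them gives no loss rate.

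The schedule of events has laboratory tests on treatment only at Weeks 4 and 12, so a draw at any other time in the treatment period is unscheduled unless it is an ET value.

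Example: neutrophils are 0.8 at Week 4, drug is held, and the count has recovered at the repeat. If the repeat is treated as the Week 4 retest, the Week 4 summary and shift tables show only the recovered value.

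**4. Cover from other tables.**
- Protocol 7.3.4 makes a laboratory change an AE when it is significant, with no numeric limit. Protocol 7.6.5 asks for the diagnosis rather than the test where possible.
- Severity in Protocol 7.6.4.2 is defined by symptoms and daily activity. A neutropenia TEAE therefore does not show whether the hold or the stop limit was crossed.
- Disposition gives reasons for leaving the study. It is not planned by laboratory limit and does not cover holds that end in resumption.
- Protocol 4.4 requires the reason for each interruption in the case report form, but SAP 11 does not tabulate it.

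**The case against.** The strongest reply is that nothing promised is missing. Protocol 8.3.3 asks for descriptive statistics by visit, and SAP 13.2 delivers these and adds shift tables and listings of abnormal results. The limits in 4.4 are dosing rules for individual subjects, not endpoints. Listings are ordered by treatment group (SAP Appendix 1), so a reader can count by hand. An independent DSMB reviews unblinded safety data by arm at least three times (Protocol 4.5). The Phase 1b study saw no clinically significant laboratory changes (Protocol 2.1.2). Replacing a spurious value by its retest is also reasonable.

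Most of this stands. It shows that no rule is broken and no data are lost. It does not show that the planned tables answer the question, or that the retest rule is harmless when the retest follows a hold.

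Four stronger readings are tempting and are not supported:
- **That low platelets and raised AST/ALT go uncounted.** They are absent from the named TEAE lists, but all TEAEs are tabulated by preferred term, and a value that forces a hold would ordinarily be judged significant.
- **That triggering values always drop out.** Two of the situations above keep them. The retest step is written into the hold rule only; the stop rule has none.
- **That no table will ever hold this count.** The layouts were not available, so the point concerns what the SAP specifies.
- **That the loss can be sized from assumed event rates.** The chance of at least one affected subject in an arm, at a guessed rate, does not measure information lost.

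**Conclusion.** The point holds as a cheap improvement, not as an error that biases an efficacy result or breaks a commitment in the protocol. The SAP specifies no per-arm count at any of the 8 laboratory limits. Under SAP 5.7 a triggering value can be replaced by a retest taken after drug was held, or left out because it was unscheduled, so the by-visit tables can understate laboratory toxicity. TEAE and disposition tables reduce the gap but depend on judgement and do not carry the limit.

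The size cannot be stated: the documents give neither the rate at which subjects reach the limits nor the way repeats are coded. The conclusion assumes that the separate layouts do not already supply the count. The shift-table example further assumes that shifts are classed only as normal or abnormal.

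**What to change.** In SAP 13.2, notwithstanding 5.7, add one table per arm giving n (%) of safety-population subjects, after the site 027 exclusion in SAP 3.5, with any value after first dose (scheduled, unscheduled, pre-retest or ET) that meets each limit:

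| Parameter | Hold | Stop |
|---|---|---|
| Neutrophils (x10^3/µL) | >0.5 to <1 | ≤0.5 |
| Lymphocytes (x10^3/µL) | >0.2 to <0.5 | ≤0.2 |
| Platelets (x10^3/µL) | >50 to <100 | ≤50 |
| CPK | >10 x ULN | none |
| AST/ALT | >5 x ULN | none |

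Count hold and stop separately and not exclusively: a subject with neutrophils of 0.8 and later 0.4 belongs in both. Flag values not confirmed on retest, so that confirmed and unconfirmed counts both show.

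Add baseline-to-worst shift tables, banded at these limits and at the screening cut-points where they exist:
- AST and ALT: ≤1, >1 to 2, >2 to 5, >5 x ULN
- CPK: ≤1, >1 to 10, >10 x ULN
- Neutrophils: ≥1.8, 1 to <1.8, >0.5 to <1, ≤0.5
- Lymphocytes: ≥1.0, 0.5 to <1.0, >0.2 to <0.5, ≤0.2
- Platelets: ≥125, 100 to <125, >50 to <100, ≤50

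The cost is SAP wording, one eight-row table and six shift tables from data already collected, with no new samples and no change to conduct. The drawback is a few more tables and some counted values that prove spurious, which is why the flag is needed.
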